All prisoners in the study undergo an oral examination to establish a baseline (hereafter T0) of oral health and a comprehensive questionnaire to identify risk factors and their attitude towards their oral health and oral treatment. Norwegian speaking prisoners are then randomized into either a treatment or control group. In the treatment group, dental staff initiate a conversation with the prisoner based on techniques from MI. Both groups finally receive a toilet bag with basic equipment to regularly clean their teeth. After 4 weeks and 12 weeks (hereafter T1 and T2), prisoners are invited back for another oral examination and a follow-up questionnaire, to measure changes in oral hygiene, oral cleaning routines, and attitude towards their oral health. At T1 we also conduct a screening of general learning difficulties using the validated screening tool HASI (Hayes, 2002). If the intervention proves to be an effective tool in improving oral hygiene, oral cleaning routines, and/or attitude towards own oral health, it can serve as an alternative proactive approach to improve oral health of a vulnerable group in society. If the improvements in oral hygiene and oral cleaning routines are long lasting, this may in turn lead to a reduced need of oral treatment. An improved attitude towards own oral health may, together with other rehabilitation programs in prison, improve the prisoner's self-esteem and chances to successfully returning to society after having served their prison sentence.

Study Design

Hypothesis:

H1: The conversation based on Motivating Interviewing (hereby the intervention) leads to a reduction in observed plaque and gingival inflammation for prisoners.

H2: The intervention leads to improved reported cleaning routines of prisoners in general, and particularly brushing of teeth.

H3: The intervention leads to a reduction in prisoners' intake of food and drinks in total, and particularly in-between meals.

H4: The intervention leads to improved perceptions about the prisoner's oral health. It improves how they view their oral health, they consider their oral health as more important, they report an increased wish to improve it, and they have increased efforts to improve it.

H5: The intervention leads to an increase in number of questions the prisoner asks during their visit with the dental staff, suggesting an increase in curiosity concerning their oral health.

Treatment effects and measurements:

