We expect that there will be somewhat high attrition of reasons independent of the intervention. The major reason for attrition is that the prisoner is released from prison sometime between T0 and T1 or between T1 and T2. We do not have capacity or legal rights to follow the prisoner outside of prison, and even if we did it would be hard to get the newly released prisoners to prioritize a follow-up oral examination and questionnaire outside of prison. Another potential reason for attrition is that the prisoner is transferred to a prison outside of Rogaland County. We do not have the capacity to follow a prisoner outside of Rogaland County. However, we do follow-up oral examination and questionnaire on prisoners who are transferred within prisons in Rogaland County.

As participation is voluntarily, prisoners can withdraw their consent, or choose not to show up for T1 and T2. This is a common problem for most RCTs in social science. As subjects in our population is serving time in prison, they have limited alternative activities to engage in, which is likely to somewhat reduce the number of prisoners who choose not to show up at T1 and T2 (except for reasons explained above).

Expected timeline

Data collection started in November 2021 and is likely to continue until the beginning of 2023. We have funding to collect data one day a week for one year in each prison. In the event that we are unable to recruit enough prisoners one of the prisons, resources can be reallocated to one of the other prisons. We have applied for additional funding to extend data collection for an additional two to three months.

We are estimating to recruit around 500 prisoners to the study, based on the capacity we have available in the project. However, the pandemic and access to prisoners makes this estimate very uncertain.

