The end date for data collection depends, in addition to uncertainty regarding whether additional funding is approved, on the extent that the ongoing pandemic will affect data collection. If stricter infection control measures are enforced, prisons are likely to quickly deny access for external partners. The new omicron variant of the corona virus has already forced delays in three out of four prisons. During a period in which we are not allowed to enter a prison, we will be forced to do follow-up examinations at times deviating from the times described above and our flow chart presented below. We are also likely to experience higher attrition during such periods, as prisoners are released or moved to a prison outside Rogaland County before we are allowed to do follow-up examinations. Such attrition is independent of treatment status. During periods we are not allowed to enter the prison, dental staff will work in their regular clinic instead. Therefore, we are not spending project resources during lockdowns.

During the data collection period we are aiming to recruit around 500 subjects. The number of subjects we can recruit depends on several factors. First, we rely on enough people serving their prison sentence during the data collection period. We know that prisons in Rogaland County have not been fully occupied in recent years. Second, the proportion of prisoners who choose to participate is uncertain. Third, time spent on each prisoner depends on how effectively the prison staff can bring prisoners to the examination room and how effective the routines of dental staff are. Forth, we do not know many of the prisoners have sufficient Norwegian language to participate in the study. See the power calculation section for a more detailed discussion about the required sample size.

[figure not shown]
Each prisoner is followed for 12 weeks in total, and we continuously recruit prisoners in the data collection period. The intervention occurs only at time T₀, and only for those randomized to the treatment group. During the first few months we recruit primarily those who are already imprisoned, and once all of them have been given the chance to participate, we start recruiting new prisoners.

Intervention

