The main covariate included in the analysis is the pre-intervention MPS index score. For our secondary outcome variables, the equivalent pre-treatment observation is used as covariate to control for pre-intervention status. We include these as they are likely to explain a lot of the variation in the outcome variable. Furthermore, we include a dummy variable for each prison, to control for prison-specific variation, and a dummy variable for the person who completed the MI-intervention with the prisoner.

As described below, we will also conduct heterogeneous analysis. Covariates that are relevant for such analysis (HASI and depressive symptoms) will also be included in the overall analysis.

Other covariates may be included, however given that we have successfully randomized prisoners, they should not affect our results. For robustness purposes, we will run analysis that include individual-specific covariates such as age, education, and length of prison sentence.

Heterogeneous analysis:

We will study heterogeneous effects of the intervention depending on their baseline score of the primary outcome variable. Those who score high on level of plaque have the greatest improvement potential. However, they might also be those with the least interest in taking care of their oral health. As motivational interviewing is designed to also motivate those who are not motivated, they may still experience the greatest improvement from the intervention.

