Moreover, we will study heterogeneous effects of the intervention depending on the prisoner's score on the learning ability screening test (HASI). The minimum and maximum score on the screening test is 45,7 and 96,4 points, respectively. HASI suggests that the border line of 85 should be used to indicate possible intellectual disabilities. However, when Søndena et al. (2008) validated the Norwegian translated version of the test on a sample of prisoners in the Norwegian Correctional Service, they found that this cut off provided many false positive cases compared to the more comprehensive Wechsler Abbreviated Scale of Intelligence (WASI). They suggested a lower cut off score of 80 to avoid too many false positives. We will study heterogeneous effects using both these cut offs in separate regressions, constructing dummy variables that separate those below or above the cut off, and interact these dummy variables with the treatment variable. There are two main reasons why we might expect (or not expect) a heterogeneous effect of the intervention for these groups. Motivational interviewing is developed to help patient groups that do not respond to traditional therapy, suggesting that prisoners with possible intellectual disabilities may still benefit from the intervention. On the other hand, however, scoring low on the ability screening may make it more difficult to benefit from the from the MI-based conversation and to use it as a basis for change.

Finally, we are going to study heterogeneous effects of the intervention depending on the prisoner's depressive symptoms, measured by MHI-5. We expect those with stronger depressive symptoms to respond less to the intervention, as they are less likely to be in a state where they prioritize their oral health and to benefit from the MI-based conversation. We collect MHI-5 at both T0, T1 and T2. As MHI-5 at T1 and T2 may be correlated with the intervention, we must use MHI-5 measured at T0 as

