The covid-19 pandemic is still ongoing at the start of data collection. Even though everyone in Norway have been offered two doses of the vaccine when data collection started, new variants of the virus and larger outbreaks of existing variants are likely to cause delays and possibly missing data. The omicron variant of the virus has already forced temporary suspension of data collection, and we expect to have follow-up observations at times different from what is stated in the flow chart, and missing observations as prisoners have been released from prison or transferred to a different prison prior to follow-up observations (especially during a temporary suspension of data collection). These issues occur independent of whether the prisoner is in the treatment group or not.

Delay in data collection due to temporarily suspension of the trial, may force us to redefine the follow-up periods from 4 and 12 weeks to a range of weeks such as 4-6 and 12-15 weeks. Despite making the follow-up periods more flexible, we are likely to have observations delayed even beyond this, leading to missing data. Additionally, as already mentioned, we are likely to have missing data due to prisoners being released or transferred to a prison that is not part of our study. To partially account for this, we will consider multiple imputations and/or maximum likelihood estimation to replace missing data.

Although we are unlikely to experience non-compliance of treatment prior to the time of the intervention, there is a real concern about attrition between the intervention and the follow-up observations. We can only speculate on reasons to why they choose not to participate any further. Prisoners are in a vulnerable position, and many of them have severe health issues stopping them from participating. They might also be busy working or studying, find it unnecessary (less informative) to see dental staff multiple times, choose not to prioritize it at the expense of leisure time or other activities, and so on. Importantly, attrition may be correlated with the intervention itself.

We carefully note any missing data and separate reasons depending on whether it is due to the prisoner being released from prison, moved to a prison outside our trial sites, temporary suspension of data collection due to the pandemic, if they choose not to meet at T1 or T2 despite still being available in the prison, or any other reason.

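### HASI, measured only at T1, is a covariate in the overall-effect regressions, so complete-case T2 models would drop observed outcomes and condition on T1 attendance

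*Combined protocol and SAP*

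**What the plan says.** Four parts of the plan bear on this.

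- **Timing of HASI.** The Project summary says: "At T1 we also conduct a screening of general learning difficulties using the validated screening tool HASI". No T0 HASI measurement is described anywhere.
- **Timing of the intervention.** Under Expected timeline: "The intervention occurs only at time T₀, and only for those randomized to the treatment group". HASI therefore follows both randomisation and the intervention.
- **Role of HASI.** The Covariates section, after pointing ahead to the heterogeneity analysis, says: "Covariates that are relevant for such analysis (HASI and depressive symptoms) will also be included in the overall analysis". Statistical model specification makes the adjusted models ordinal logistic regressions and the overall tests unadjusted Wilcoxon-Mann-Whitney tests. It names T1 as the time point of primary interest.
- **Attendance and missing data.** Under Withdrawal criteria, "prisoners can withdraw their consent, or choose not to show up for T1 and T2". Other issues adds: "Importantly, attrition may be correlated with the intervention itself". The same section says that multiple imputation and/or maximum likelihood will be considered. It commits to neither and does not mention missing HASI.

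For the other moderator, Heterogeneous analysis takes a firmer line: "As MHI-5 at T1 and T2 may be correlated with the intervention, we must use MHI-5 measured at T0 as" the basis for differential effects. The plan gives no corresponding statement for HASI, and it does not say which MHI-5 measurement enters the overall model.

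**The concern.** A covariate in a model for a randomised comparison should normally be fixed before randomisation. Otherwise the set of people analysed, or the covariate itself, can depend on what happened after allocation. HASI exists only for prisoners who came to T1 and completed the screen. A prisoner who missed T1 but was examined at T2 has an outcome and no HASI score, and software that fits complete cases will drop that person without comment.

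Two things are at stake, both mainly at T2. The first is precision: the plan already expects more missing data at T2 and doubts whether it could tell a fading effect from low power there. The second is selection: the adjusted T2 estimate would describe those who attended T1 as well as T2, although T1 attendance is not needed to observe the T2 outcome.

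**Working it through.** **Who is lost, by model**

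| Model | Outcome needs | HASI needs | Extra loss caused by HASI |
|---|---|---|---|
| Wilcoxon-Mann-Whitney, T1 or T2 | that visit | not used | none |
| Adjusted regression, T1 | T1 attendance | T1 attendance and completed screen | T1 attenders without a HASI score |
| Adjusted regression, T2 | T2 attendance | T1 attendance and completed screen | T2 attenders who missed T1 or have no HASI score |

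The last column assumes complete-case fitting.

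**Precision**

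The plan gives no rate of missing HASI; on attrition in general it says only: "We expect that there will be somewhat high attrition of reasons independent of the intervention". The loss L is therefore assumed at 10% or 20% of analysable prisoners. The share of residual variance explained by HASI, R², is assumed at 0 or 2%. With a linear model standing in for the ordinal one,

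SE ratio = √[(1 − R²)/(1 − L)]

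- L = 10%: √(1/0.90) = 1.054; √(0.98/0.90) = 1.043.
- L = 20%: √(1/0.80) = 1.118; √(0.98/0.80) = 1.107.

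The standard error rises by about 4-5% and 11-12%.

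**The same loss on the plan's own power scale**

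Power calculations gives total sample sizes of 106 (effect size 0.5) and 320 (effect size 0.286) at alpha 0.05 and power 0.8. Both reproduce exactly from noncentral-t power with relative efficiency 3/π, 1:1 allocation and one-sided alpha. The plan does not state sidedness; two-sided alpha gives 134 and 404. These figures belong to the Wilcoxon test, which HASI does not touch, so they serve only as a yardstick for losing observed outcomes.

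| Assumed loss | Power, N = 320 | Power, N = 106 | N to recruit so that 320 remain |
|---|---|---|---|
| 0% | 0.802 | 0.803 | 320 |
| 5% | 0.784 | 0.785 | 320/0.95 → 337 |
| 10% | 0.764 | 0.765 | 320/0.90 → 356 |
| 20% | 0.721 | 0.721 | 320/0.80 → 400 |

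**Bias**

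This was illustrated by simulation with every input assumed: 200,000 prisoners, a continuous T2 outcome, a true effect of −0.286, an unobserved motivation variable related to both HASI and outcome, and 18-20% missing T1. The treatment coefficient from the HASI-adjusted model was:

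| T1 attendance | Everyone | Only those with HASI |
|---|---|---|
| unrelated to arm and motivation | −0.285 | −0.283 |
| moderate arm-by-motivation dependence | −0.290 | −0.329 |
| strong arm-by-motivation dependence | −0.283 | −0.361 |

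The simulation error of a coefficient is roughly 2/√200,000 = 0.0045 when the outcome SD is about 1. The first row therefore shows no bias, and the other two rows do. The direction follows from the assumption that more motivated treated prisoners attend more often; it is not a prediction for this trial.

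**The case against.** The case against is strong on scope, and most of it stands.

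- **T1 is of primary interest, and HASI belongs to the same visit.** This stands. A reader might infer that the main adjusted estimate becomes conditional on T1 attendance because of HASI. At T1 it is conditional on attendance with or without HASI; only non-completion of the screen adds anything, and nothing in the plan suggests that this is common.
- **The overall tests are unadjusted.** This stands. The point concerns the ordinal regressions only. In the individual fixed-effects robustness models, a score measured once is absorbed in any case.
- **Imputation may be used.** This stands in part. Dropping these prisoners is not certain, but imputation is neither promised nor specified for HASI.
- **Few prisoners may be affected.** Release, which the plan calls the major cause of attrition, and transfer out of the county would usually remove both visits. Seen at T2 but not at T1 arises mainly from no-shows and lockdown gaps, and a delayed T1 visit could still yield a HASI score. This is why the share is treated as unknown.
- **HASI is a stable trait.** A reader might infer that adjusting for HASI removes part of the treatment effect, or that the plan's reason for using T0 MHI-5 carries over directly. Neither is supported. That reason concerns a measure that may respond to the intervention, and one conversation of up to 30 minutes is unlikely to change a learning-ability score much. Stability does not, however, answer the loss of outcomes or the selection.
- **Unblinded staff.** A reader might also infer that HASI is scored by staff who know the arm. The Blinding section says only that staff might still remember it. Other issues does call them not blind at later visits but also provides for new examiners. The plan does not say who administers HASI, so the point does not rest on this.

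**Conclusion.** The concern holds for the adjusted T2 regressions under complete-case fitting. There, including HASI discards observed outcomes and makes the estimate conditional on T1 attendance. At T1 the effect is confined to attenders without a completed screen.

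The size cannot be established from the plan. The percentages above rest on assumed losses and on a linear approximation that does not carry over exactly to ordinal logistic regression. Loss of precision follows from any missing HASI. Added bias needs more: T1 attendance must depend on arm together with prognosis. The plan's acknowledgement about attrition makes that possible but does not show it. It would be wrong to conclude that the trial's overall result is biased. The supported conclusion is that an avoidable dependence has been built into one set of adjusted models, at the visit where data are expected to be scarcest.

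**What to change.** In the Covariates section, remove HASI from the overall-effect regressions and use it only in the HASI heterogeneity models. If wanted, keep a version of the overall model with HASI as a labelled sensitivity analysis. State in the same place that MHI-5 in the overall model is the T0 value; the separately planned analysis of changes in depressive symptoms, which the plan already describes as endogenous, can stay as it is. The other covariates listed there, including the dummy for the person who delivered the MI conversation, are outside this change.

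The cost is about one sentence and whatever small share of outcome variance HASI would have explained. No data collection changes, and the planned HASI heterogeneity analysis is kept. The plan says it was written before any data analysis, so the change can be made on principle if it is made before analysis begins. This is a free improvement.

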The main variable of interest and primary outcome measure of the treatment effect is the mucosal-plaque index (MPS). It consists of the sum of a four-point plaque score (PS) and a four-point mucosal score (MS). For the PS, score of 1 suggests no visible plaque, score of 2 suggests plaque is barely visible, score of 3 suggests a moderate amount of plaque, and score of 4 suggests large amount of plaque almost covering the whole surface of teeth. For the MS, score of 1 suggests normal mucosal, score of 2 suggests mild inflammation, score of 3 suggests medium inflammation, and score of 4 suggests strong inflammation. For both scores, if in doubt between 1 and 2, they are instructed to score 1. If in doubt between 3 and 4, they are instructed to score 4.

The index is designed to evaluate oral health and oral hygiene in groups of individuals, developed for use in institutions. This makes it a suitable index to be used when conditions are not optimal to assess the patient. In prison, dental staff have limited equipment and poor light compared to conditions at a dental clinic. It was therefore important to use an index designed to be used outside of dental clinics with less optimal conditions for oral examination.

The secondary measures of outcome are based on questionnaire responses. These are questions asked both prior to treatment and during the follow-up period, and measures changes in how the prisoner perceives his oral health, how his routines are for maintaining his teeth, and his intake of food and drinks. How these questions are formulated can be seen from the questionnaire directly. These questions are designed to measure behavioral changes because of the intervention. As the questions are identical at each meeting point, any difference in changes across the treatment and control group is likely to be a result of the intervention. Importantly, even though the MPS-index may not measure a significant change in oral hygiene, such behavioral changes may still be of great importance. For example, even though a prisoner does not change his cleaning routines and is unable to improve his plaque score, a reduction in intake of unhealthy food and drinks may still reduce the damage on his teeth. Likewise, an improved perception about their oral health, may still improve self-esteem, even though there is no reduction in plaque score.

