In addition, as a secondary outcome measure, dental staff take notes of how many times the prisoner asks questions about his teeth. If the intervention successfully increases the prisoner's interest in his own oral health, we could expect more questions about his oral health.

Basic methodology:

The study is a randomized control trial (RCT), testing an MI-based intervention on oral health (oral hygiene) for prisoners in Rogaland County, Norway. More details about the population and the intervention follows in subsequent sections.

We randomize prisoners into treatment or control groups, blocking at prison level, using the randomization tool at www.randomizer.org. See the randomization section for more details on the randomization process. Moreover, we blind prisoners from treatment status, and dental staff is either blind to treatment when doing the oral examinations, or the oral examination is conducted by two dental staff independently of each other. See the blinding section for more details on blinding.

Study design and procedures:

Geographic region

The geographic region of this study is Rogaland County in southwestern part of Norway. Rogaland County is the wealthiest county in Norway measured in terms of household income (2019, SSB). Despite being one of the wealthiest counties in Norway, growing up in Rogaland is similar to growing up in other counties in Norway. An important reason for this is the unitary and federally funded school system, with only a few ideological or pedagogical based private schools. This gives all children growing up in Norway similar opportunities to obtain an education and subsequently enter the labor market.

Research population

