Clinical data will include information on decayed, missing and filled teeth (DMFT). This data will only be collected at T0, as it is not possible to observe any change during the follow-up period. Moreover, we will collect clinical data on plaque and mucosal inflammation, using the MPS index. This is our main variable of interest. Plaque is affected by oral hygiene routines and the intake of drinks and food that can damage teeth, and thus any observed difference in changes in plaque between the treatment group and the control group may be interpreted as an effect of the intervention. Dental staff has undergone a calibration exercise of both DMFT and MPS.

The questionnaire is extensive. It starts with some background questions about demographic and socio-economic status, which are not likely to change during the follow-up period, and thus only asked at T0. Next, we ask questions about their views on their own oral health. In particular, we ask them about how they perceive the condition of their own oral health, whether they want to improve it, whether they regularly visit a dentist outside of prison, their cleaning routines and their intake of food and drinks. Some of these questions are secondary variables of interest. In the case of an intervention effect, prisoners may have an adjusted view on their oral health, and they may change their oral cleaning routines and intake of food and drinks. We also ask them standardized questionnaires about their oral-health quality of life (OHIP-14) and their self-reported anxiety and discomfort to dental treatment (Corah). As these are unlikely to change during the follow-up period, they are only asked at T0.

We also collect data on their general physical and mental health. To measure mental health, we use the standardized questionnaire Mental Health Inventory 5 (MHI-5). We conduct the MHI-5 questionnaire at all meeting points, T0, T1 and T2, as we expect reduced effects of the intervention if they are experiencing worsened mental health. This may be important when studying heterogeneous effects of the intervention. Lastly, we collect data on their alcohol and drug use (outside of prison), using the short versions of alcohol use disorders identification test (AUDIT-4) and the drug use disorders identification test (DUDIT), collected only at T0.

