basis for differential effects in this analysis. The scale of MHI-5 is 0 (poor mental health) to 100 (good mental health). In the literature, the most frequent cut offs used to describe depressive symptoms seems to be 52 points (severe depressive symptoms), 60 points (moderate or severe depressive symptoms), and 68 points (mild, moderate, or severe depressive symptoms). We expect the number prisoners with depressive symptoms to be substantial. In a study of prisoners in the Norwegian Correctional Service, Friestad & Kjelsberg (2009) showed that 27% of the prisoners had mental health problems of significant intensity (classified as “psychiatric case” using the Hopkin Symptom Checklist). We are going to study the interaction effect between MHI-5 and the treatment in two ways. One way is to create dummy variables based on the cut offs suggested above and run separate regressions for each cut off (interacted with the treatment variable). The other approach is to include the MHI-5 variable as a continuous variable and interact it with the treatment variable. For the latter case to have a correct specification, MHI-5 would need to have a linear relationship to the dependent variable, which may not be realistic. One might think that those with more severe depressive symptoms are substantially more affected than those with very mild depressive symptoms. Adding a squared term of the MHI-5 variable will account for a potential quadratic relationship to the dependent variable. Additionally, we will run analysis to control for changes in depressive symptoms when studying the overall effect of the treatment. As the variation in depressive symptoms between T0, T1 and T2 may be correlated with the treatment, this will be an endogenous analysis that might still shed some light under which conditions the treatment works.

Other issues:

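### Controlling for the post-randomisation change in MHI-5 cannot show when the treatment works, and if treatment moves MHI-5 the adjusted coefficient has no clear meaning

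*Combined protocol and SAP*

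**What the plan says.** The plan uses MHI-5 in two ways in its Heterogeneous analysis section.

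- **As a moderator.** It restricts this use to baseline: "As MHI-5 at T1 and T2 may be correlated with the intervention, we must use MHI-5 measured at T0 as" the basis for differential effects. T0 MHI-5 is then interacted with treatment, both through cut-offs and as a continuous score.
- **As a control.** The section closes with a further step: "Additionally, we will run analysis to control for changes in depressive symptoms when studying the overall effect of the treatment". It grants that "As the variation in depressive symptoms between T0, T1 and T2 may be correlated with the treatment", and concludes that "this will be an endogenous analysis that might still shed some light under which conditions the treatment works". It gives no equation, interaction term, mediation estimand or identifying assumptions for this step.

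The section on data collection explains why the scale is repeated: "We conduct the MHI-5 questionnaire at all meeting points, T0, T1 and T2, as we expect reduced effects of the intervention" when mental health worsens. That is a hypothesis about effect modification.

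MHI-5 at T1 and T2 is not an outcome. The hypotheses H1 to H5 do not mention it. The questionnaire-based secondary outcomes are described as items whose repetition "measures changes in how the prisoner perceives his oral health, how his routines are for maintaining his teeth, and his intake of food and drinks". The one other secondary outcome is a count: "as a secondary outcome measure, dental staff take notes of how many times the prisoner asks questions about his teeth".

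**The concern.** The purpose and the model do not match. The purpose is to learn when the conversation helps. The model, as worded, holds MHI-5 change fixed and reports one overall effect, which says nothing about whether that effect differs between prisoners whose mental health improved and those whose mental health worsened.

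The section has also just ruled out T1 and T2 MHI-5 as a basis for differential effects because treatment may influence them. The closing step brings the same measurements back for a question of the same kind.

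At stake is a second overall-effect estimate, reported beside the unadjusted one. If the two differed, the gap could be taken as a finding about mental health when it might reflect only conditioning on a variable that treatment had altered.

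**Working it through.** The documents give no figure for the effect of treatment on MHI-5 or for the association between MHI-5 change and MPS. There is therefore no planned figure to reproduce. The power calculations do not bear on this point.

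**1. Can the control term show conditions?**

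Take a true model with treatment T, MHI-5 change M (mean zero, independent of T) and an interaction k:

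Y = −0.286·T − 0.3·M + k·T·M + error

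Fit Y on T and M without the interaction. The coefficient of T is then −0.286 + k × mean(M) = −0.286, whatever k is. Simulation with 1,000,000 subjects per case gave:

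| True interaction k | Fitted coefficient of T |
|---|---|
| 0 | −0.284 |
| +0.3 | −0.283 |
| −0.3 | −0.290 |

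Three different patterns of effect modification give practically the same answer. The value −0.286 echoes the lowest effect size in the plan's power section; the other coefficients are assumed.

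**2. What does the adjusted coefficient estimate?**

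All inputs here are assumptions, in SD units and in a linear model. Lower MPS is better and higher MHI-5 is better.

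- M = a·T + g·U + error, with variance 1 within arm
- Y = −0.30·T − g·U + error
- U is an unmeasured cause of both, with variance 1. M has no causal effect on Y.

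Within arm, Cov(M, Y) = −g², so the coefficient of M is −g². The adjusted coefficient of T is −0.30 − a × (−g²) = −0.30 + a·g².

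| a | g = 0.3 | g = 0.5 |
|---|---|---|
| 0 | −0.300 (0%) | −0.300 (0%) |
| 0.05 | −0.30 + 0.0045 = −0.2955 (1.5%) | −0.30 + 0.0125 = −0.2875 (4.2%) |
| 0.2 | −0.30 + 0.018 = −0.282 (6%) | −0.30 + 0.050 = −0.250 (17%) |
| 0.3 | −0.30 + 0.027 = −0.273 (9%) | −0.30 + 0.075 = −0.225 (25%) |

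The percentage is the share of the true effect lost. Simulation with 2,000,000 subjects gave −0.281 and −0.250 for a = 0.2, and −0.272 and −0.224 for a = 0.3, each within 0.001 of the formula.

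**3. Other structures**

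- *MHI-5 also affects MPS* (coefficient −0.3, shared-cause loading 0.4, direct effect −0.286, a = 0.2). The total effect is −0.286 − 0.06 = −0.346. The coefficient of M is −0.3 − 0.16 = −0.46, so the adjusted effect is −0.346 + 0.2 × 0.46 = −0.254 (simulated −0.253). This is neither the total effect (−0.346) nor the direct effect (−0.286). With a = 0.4 the shift is 0.4 × 0.46 = 0.184.
- *MPS affects MHI-5.* Both are measured at the same visit, so this direction is possible. Let M = h·Y + error, with unit error variances. The adjusted effect is then the total effect divided by (1 + h²). For a total of −0.50 this gives −0.50/1.04 = −0.481 at h = −0.2 and −0.50/1.16 = −0.431 at h = −0.4 (simulated −0.482 and −0.433).
- *Treatment moves MHI-5 neither directly nor through MPS.* The simulated shift was zero to within 0.001 in every case.

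**4. Would an interaction rescue it?**

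No. If treatment influences who improves on MHI-5, prisoners in the two arms with the same change score are no longer comparable. This is the reason the section gives for using T0.

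**The case against.** The authors saw the problem. They present the regression as an addition, call it endogenous, claim only that it might shed some light, and put the valid T0 interactions first. The text also gives no equation, so the absence of an interaction is inferred from the wording. All of this stands, and it limits the weight of the point. It does not remove it: a caveat about bias does not make a main-effect model answer a question about effect modification, and the interacted version fails by the plan's own rule.

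A reader might go further than the documents allow in four ways.

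- **That the adjustment necessarily biases the effect.** The plan says only that MHI-5 change may be correlated with treatment. Without such an effect the shift is zero in the linear model.
- **That a loss of 6% to 25% is to be expected.** Those values need a = 0.2 to 0.3. That would give one conversation of up to 30 minutes an effect on general mental health about as large as the smallest plaque effect the plan cites (0.286). The range has to start at 0%. The plan's regressions are also ordinal logistic, so the linear figures indicate only direction and rough order.
- **That leaving MHI-5 out of the outcomes is an error.** H1 to H5 make no mental-health claim. The plan mentions self-esteem as a possible benefit, but nowhere says that MHI-5 measures it.
- **That T0 MHI-5 should be the only heterogeneity analysis of any kind.** Nothing here counts against the planned analyses by baseline MPS and by HASI.

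**Conclusion.** The point holds as a minor correction to a supplementary analysis. That a main-effect control cannot show conditions rests on no assumed number. The distortion of the coefficient is conditional: it arises if treatment moves MHI-5, directly or through the outcome, and MHI-5 affects or shares causes with MPS. Under the shared-cause assumptions in step 2 it is 0 to about 0.075 SD, or 0% to 25% of an effect of 0.30. The other structures tried gave up to about 0.18 SD, part of which is a mediated effect rather than confounding. None of these inputs comes from the documents.

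The primary Wilcoxon comparison and the T0 MHI-5 interactions are unaffected.

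**What to change.** 1. Delete the regression that controls for change in MHI-5. Alternatively, relabel it as an exploratory mediation analysis, state its estimand and assumptions (including no unmeasured common causes of MHI-5 change and MPS, and the assumed direction between them), and remove the claim about conditions.
2. Keep T0 MHI-5 by treatment as the only MHI-5 analysis of conditions. Leave the baseline-MPS and HASI heterogeneity analyses in place.
3. As an inexpensive improvement, and not the correction of an error, compare MHI-5 between arms at T1 and at T2 as an exploratory outcome, adjusted for T0 MHI-5 and prison, with a 95% CI. Randomisation supports this comparison, subject to attrition. It also helps show whether treatment moves MHI-5 at all.

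The cost is a change of wording in the plan. It needs no new data and no change to the sample size. The downside of item 3 is one more exploratory outcome to label as such.
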